All patients treated on this protocol will have developed metastatic disease. It is plausible that up-regulation of MHC class I with either radiation therapy or intralesional IFN β -1B injection may have an independent effect on the targeted metastasis (as assessed by RECIST criteria). It is unlikely however, that localized radiation or intralesional interferon will have a significant effect on the risk of distant disease development. In contrast, T-cell infusions and/or anti-PD-L1 have the potential to generate a broader systemic effect by preventing the occurrence of new distant metastasis. To assess the potential systemic effects of adoptively transferred T cells, the time for a new metastasis to develop after treatment will be assessed, and this parameter will be compared to historical matched controls undergoing standard therapy. A preliminary assessment was carried out on 49 of the MCC patients in our cohort who originally presented with local or regional disease and later developed metastatic disease, at which time they underwent standard therapy (radiation or chemotherapy). Patients with systemic immune suppression were eliminated from the analysis as they would not be candidates for the combined MHC and T-cell therapy trial. Among these patients, the median time to developing a new metastasis was 200 days (see **Section**

18 for further statistical details). Patients will be followed and restaged at least once every 3 months and as clinically indicated after 12 months since the last infusion has elapsed until new metastasis occur (see **Appendix B**).

12.D.2 Clinical response by RECIST criteria (secondary endpoint)

Tumor lesions and tumor responses will be assessed according to the **Response Evaluation Criteria in Solid Tumors (RECIST) v 1.1**. Radiographic imaging and clinical assessment of residual disease will be compared with pre-infusion assessment.

Responses will be reported separately for lesions which did or did not receive MHC Class I upregulation interventions, if the latter are present. Overall responses will be reported as well.

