Clinical response assessment of each individual lesions: Response assessment will be done through clinical (for example bi-directional measurements of palpable lesions) or radiographic (for example CT, PET, or MRI) measurement of each lesion at 8 weeks after the first intervention to induce MHC class I upregulation, 8 weeks after the second MHC class I upregulation, if the patient undergoes a second set of T cell infusions, and then at least once every 3 months (12 weeks) or as clinically indicated. Consistency of imaging modality over time is recommended for a given patient. Objective responses in lesions which received MHC Class I upregulation and lesions which did not receive MHC Class I upregulation, will be reported separately. For each individual lesion or group of lesions, a complete response (CR) will be defined as total regression of the lesions, a PR as 30% or greater decrease in the sum of the longest diameter of the lesions compared to baseline and PD as 20% increase in the sum of the longest diameter of the lesions compared to the smallest prior diameter (RECIST v1.1 criteria).

Overall Response Assessment:

A complete response (CR) will be defined as total regression of all tumors, a PR as 30% or greater decrease in the sum of the longest diameter of target lesions compared to baseline and PD as 20% increase in the sum of the longest diameter of target lesions compared to the smallest prior diameter (RECIST v1.1 criteria). This assessment will be performed 8 weeks after the first MHC class I upregulation, 8 weeks after the second MHC class I upregulation, if the patient undergoes a second set of T cell infusions, and then at least once every 3 months (12 weeks) or as clinically indicated.

12.E. Evaluation of Persistence and Function of Adoptively Transferred T Cells

12.E.1. Blood samples

Patients will have 50-60 ml of heparinized blood (green top) and 6 ml of serum (red top) tube drawn during the pre-treatment visit, prior to Avelumab infusion, prior to receiving radiation or intralesional IFN β -1B injections (pre-treatment baseline), prior to tissue biopsy or aspiration, prior to infusion, and at selected time points following infusion (**Appendix B**, research labs). Samples will be used to evaluate the duration of *in vivo* persistence and function of infused T cells, as well as evaluation of MCPyV TAg titers.

All blood samples will be kept at room temperature and sent to room E1-305, FHCRC Research Cell Bank.

12.E.2. Tumor samples

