18. STATISTICAL CONSIDERATIONS

The **primary objective** of this trial is to assess and compare the safety and potential efficacy associated with treating patients who developed metastatic MCC by combined MHC up-regulation and anti-PD-L1 antibody treatment (Group 1); and combined MHC up-regulation, anti-PD-L1 antibody treatment, and adoptive transfer of MCPyV TAg-specific polyclonal autologous CD8⁺ T cells (Group 2). The treatment for each group will be considered to have an acceptable safety profile, if the observed toxicity rate is consistent with a true rate that does not exceed 30%, whereas toxicity is defined in **Section 13**. The potential efficacy of treatment within each group will be assessed primarily by examining the time from first to second metastasis. Among 49 patients who would be considered eligible for this trial and who received standard treatment (localized radiation or chemotherapy) at UW, the median time to second metastasis was an estimated 200 days (**Figure 146**). This is the benchmark that we shall use in the current trial for assessment of potential efficacy.

[figure not shown]

Figure 146. Observed and predicted times to second metastasis

A total of 20 patients will be treated in the trial, including 10 in each of Groups 1 and 2 as long as the level of safety is deemed to be acceptable. This number was not derived based on any formal statistical considerations; rather, it is a number that is a compromise between the number of patients that can be enrolled in a reasonable time frame and the number of patients whose treatment will provide enough information to gain a preliminary assessment of efficacy. From our database of over 850 patients, we are in active contact with ~300 living MCC patients. Approximately 120 new patients are recruited each year to our cohort. One-third of MCC patients will have a first metastasis within 3 years of diagnosis. Each year, approximately 40 patients in our cohort experience a first metastasis. Because we now have tetramers that cover >80% of MCC patients based on their HLA alleles, we anticipate that generation of functional tetramer-positive MCPyV-specific T cells from the peripheral blood will be feasible on a sufficient number of cases so that we can readily meet targeted enrollment of four cases per year.

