APPENDIX B

Group 1 Monitoring Schedule^a

GROUP 1		Event	History and PE	Chemistry Panel	CBC	T3 FT4 TSH	Tumor Biopsy	Blood for Research	Radiographic Evaluation	Oncoprotein Serology
Pre-treatment		Evaluation for treatment	X	X	X	X ^f	X ^g	X	X ^b	X
	Day 0	PD-L1 infusion ^c	X	X	X			X		
Week +1/+2	Day +7 - +10	Administer Radiation OR Intralesional IFNβ-1B	X	X	X			X		
Week +2	Day +14	PD-L1 infusion	X	X	X			X		
Week +4	Day +28	PD-L1 infusion	X	X	X		X ^g	X		
Week +6	Day +42	PD-L1 infusion	X	X	X			X		
Week +8	Day +56	PD-L1 infusion	X	X	X			X		
Week +9	Day +63	Staging							X (Day 56-70)	X
Week +10	Day +70	PD-L1 infusion	X	X	X	X ^f		X		
Week +11/+12	Day +77- +80	Administer Radiation OR Intralesional IFNβ-1B (if indicated) ^d	(X)	(X)	(X)			(X)		
Week +12	Day +84	PD-L1 infusion	X	X	X			X		
Week +14	Day +98	PD-L1 infusion	X	X	X			X		
Week +16	Day +112	PD-L1 infusion	X	X	X			X		
Week +18	Day 126	PD-L1 infusion	X	X	X			X		
Week +19	Day +133	Staging							X (Day 126-140)	X
Week +20	Day +140	PD-L1 infusion	X	X	X			X		
Week +22	Day +154	PD-L1 infusion	X	X	X	X ^f		X		
Week +24	Day +168	PD-L1 infusion	X	X	X			X		
Beyond +52 weeks		Study ends	X ^e	X ^e	X ^e			X ^e	X ^e	X
Beyond +24 weeks infusion Q2 weeks for up to 1 year total on treatment		PD-L1 infusion	X	X	X			X		

Test results and procedures conducted as per standard of care may be used for eligibility determination and evaluation for toxicity.

^a The dates listed on the study calendar above are approximate as many patients are expected to reside out of state and his oncologists and laboratories may not always be able to follow the time points as dictated by the protocol.

^b Includes brain evaluation.

^c Patients may receive preferably one, but up to 3 infusions of anti-PD-L1 before the first MHC class I up-regulation intervention.

^d The MHC class I upregulation can be repeated once, at any time point, if there is radiological disease present.

Treatment must start within 4 weeks of the preceding radiological evaluation.

^e At least every 3 months for one year, every 6 months for one year then yearly and as clinically indicated.

^f at baseline, at cycle 6 and then every 6 cycles.

^gIf accessible.

Group 2 Monitoring Schedule^a

GROUP 2		Event	History and PE	Chemistry	CBC	T3 FT4 TSH	Tumor Biopsy	Blood for Research	Radiographic Evaluation	Oncoprotein Serology
Pre-treatment	Evaluation for treatment	X	X	X	X	X ^f	X ^g	X	X ^b	X
	Day 0	PD-L1 infusion ^c	X	X	X			X		

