Test results and procedures conducted as per standard of care may be used for eligibility determination and evaluation for toxicity.

^a The dates listed on the study calendar above are approximate as many patients are expected to reside out of state and his oncologists and laboratories may not always be able to follow the time points as dictated by the protocol.

^b Includes brain evaluation.

^c Patients may receive preferably one, but up to 3 infusions of anti-PD-L1 before the first MHC class I up-regulation intervention.

^d The MHC class I upregulation and infusions can be repeated once, at any time point, if there is radiological disease present. Treatment must start within 4 weeks of the last radiological evaluation. A cumulative total of 4 infusions can be administered. Radiation therapy or intralesional IFN- α -1B injection will typically be administered before the first infusion of subsequent cycles. Monitoring will end at least 20 weeks after the last infusion or with the development of new metastasis.

^e At least every 3 months for one year, every 6 months for one year then yearly and as clinically indicated.

^f at baseline, at cycle 6 and then every 6 cycles.

^gIf accessible.

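### Appendix B lists no staging between day 140 and week 52, contrary to Section 12.D and across the 200-day benchmark, and no rule dates a new metastasis, so scan timing could shift the go-forward comparison either way

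*Combined protocol and SAP*

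**What the plan says.** Three places set the imaging schedule.

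- Section 12.D.1 (primary endpoint) has patients "restaged at least once every 3 months and as clinically indicated after 12 months since the last infusion has elapsed until new metastasis occur" and refers to Appendix B. The sentence is loosely punctuated: the 12-month clause could attach to the clinically indicated scans or to the whole phrase.
- Section 12.D.2 is clear: 8 weeks after the first MHC intervention, 8 weeks after the second if a second set of T cells is given, "and then at least once every 3 months (12 weeks) or as clinically indicated".
- Appendix B, both groups, has staging on day 63 (56-70) and day 133 (126-140). The row for infusions beyond week 24 has no radiographic mark. The next mark is on the row that Group 1 labels "Beyond +52 weeks". Footnote c adds: "Patients may receive preferably one, but up to 3 infusions of anti-PD-L1 before the first MHC class I up-regulation intervention".

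On the end of follow-up, Appendix B, Group 2, footnote d says: "Monitoring will end at least 20 weeks after the last infusion or with the development of new metastasis".

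Section 18 describes efficacy as "examining the time from first to second metastasis" and reports that among 49 historical patients "the median time to second metastasis was an estimated 200 days". A group counts as potentially efficacious if the lower confidence limit of its median exceeds that fixed value. Trial time starts at first treatment, not at first metastasis. Table 8 gives power at one-sided 0.10 and 0.15 without choosing between them or naming the interval method. No section says how a new metastasis is dated, or how often the historical patients were scanned.

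**The concern.** The comparison with 200 days decides which treatment, if any, moves to the next trial. With 10 patients per group it depends on how many events are recorded by day 200, so one event moved across that day can change the decision. A metastasis that only a scan would reveal is recorded when the scan is done. If the trial's scans straddle day 200 and the historical patients were scanned on another rhythm, the same disease course would give different recorded times in the two data sets. An ineffective regimen could then pass more often than with exact dating, or an effective one less often. A site that follows the Appendix B table literally would have no scheduled scan over the stretch that contains the benchmark.

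**Working it through.** **1. Scan days at the 12-week (84-day) maximum.** The first MHC intervention follows an avelumab dose by 7-10 days, after one, two or three infusions.

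| Schedule | First scan (+56) | Last before day 200 | Next (+84) |
|---|---|---|---|
| Appendix B second staging row, then 12 weeks | 56-70 | 126-140 | 210-224 |
| 12.D.2, MHC day 7-10 | 63-66 | 147-150 | 231-234 |
| 12.D.2, MHC day 21-24 | 77-80 | 161-164 | 245-248 |
| 12.D.2, MHC day 35-38 | 91-94 | 175-178 | 259-262 |

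The 12.D.2 rows assume no second cycle. Every schedule straddles day 200.

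**2. Group 2 footnote d.** If the last infusion means the last T-cell infusion, one cycle ends on day 40 and 40 + 140 = day 180, before the benchmark. After infusion #4, 110 + 140 = day 250.

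**3. The plan's own figure.** With no censoring before day 200, a lower limit above 200 days means at most c of 10 events by day 200. Log-log limits give c = 2 at 0.10 and c = 3 at 0.15; exact limits give 2 at both; linear limits give 3 at both. Power is P(X ≤ c) with X ~ Bin(10, 1 − 0.5^(1/HR)):

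- HR 3 (p = 0.206): 65.9% and 86.8%, against 70% and 88% in Table 8.
- HR 4 (p = 0.159): 79.6% and 94.0%, against 85% and 92%.

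The 0.15 column agrees within 2 points and the 0.10 column does not. The nine-window historical curve is in a figure not shown, so this cannot be settled from the text. Both cut-offs are carried below. With exact dating and a true median of 200 days (p = 0.5), the false-positive rates are 5.5% (≤2) and 17.2% (≤3).

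**4. Curve shape.** Under proportional hazards Table 8 implies cumulative hazards of ln2, 3·ln2 and 4·ln2 at 200, 352 and 411 days. Then k = ln3/ln(352/200) = 1.943 and ln4/ln(411/200) = 1.925, so a Weibull shape of about 1.93. The course before day 200 is not given.

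**5. Sensitivity to scan timing.** Assumptions: one common time origin, no censoring before day 200, and historical scans every D days at random phase. A share f of lesions is found only by scan and dated at that scan.

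- F(t) = 1 − exp(−(t/b)^k), with b chosen so that (1−f)·F(200) + f·P(T+U ≤ 200) = 0.5, U ~ Uniform(0, D).
- Trial: p = (1−f)·F(200) + f·F(s), where s is the last scan before day 200. The false-positive rate is P(Bin(10, p) ≤ 2 or ≤ 3).
- Example, f = 0.5, D = 84, s = 133: b = 215.7, F(200) = 0.579, F(133) = 0.325, so p = 0.452, giving 9.7% and 26.2%.

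Results for k = 1.93, f = 0.5 (≤2 / ≤3):

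| Last scan | D = 84 | D = 182 |
|---|---|---|
| Day 133 | 9.7% / 26% (p = 0.452) | 2.9% / 11% (p = 0.546) |
| Day 147 | 7.1% / 21% (p = 0.479) | 1.8% / 7% (p = 0.578) |
| Day 161 | 5.0% / 16% (p = 0.506) | 1.1% / 5% (p = 0.608) |
| Day 175 | 3.5% / 12% (p = 0.533) | 0.6% / 3% (p = 0.637) |

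At the earliest possible last scan, day 126, the same formulas give 11.3%/29% (p = 0.439) for D = 84.

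Other settings:
- Constant hazard (k = 1), f = 0.5, day 133: 7.6%/22% (D = 84) to 3.1%/11% (D = 182).
- All lesions scan-only, k = 1.93, D = 84: 18%/40% at day 133, but 1.9%/7.7% at day 175.
- Power at HR 3, k = 1.93, f = 0.5, day 133, D = 182: p = 0.240, so 56%/80% against 66%/87% with exact dating.

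**6. Comparison with benchmark sampling error.** Ignoring censoring, the SE of a 49-patient median is 1/(2·f(200)·7), where f(200) is the density at day 200: 21.4 days for k = 1.93 and 41.2 for k = 1. Moving the true median by ±1 SE changes the false-positive rate from about 2%/7% to 12%/30%.

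**The case against.** The Section 12.D text requires restaging at least every 12 weeks or 3 months, so the Appendix B blank need not mean that scans are omitted. The row beyond week 24 looks abbreviated: footnote f requires thyroid tests every 6 cycles, and that row has no thyroid mark either. A reader might infer that no patient is scanned between day 140 and week 52, and the documents do not support that. What stands is a contradiction between the text and the table it cites, with no statement of which governs. Even if the text governs, step 1 still applies.

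The day-180 reading of footnote d is not forced. Twenty weeks is a minimum, avelumab is also given by infusion for up to 12 months, and Section 12.C speaks of the last T-cell or avelumab infusion. The wording is ambiguous and needs aligning; it does not show that follow-up stops early.

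Detection between scheduled scans is likely for some lesions. Patients are examined about every two weeks, some disease is palpable, calendar dates are approximate, and clinically indicated scans are allowed. For Group 1, footnote d also says "The MHC class I upregulation can be repeated once, at any time point, if there is radiological disease present"; a repeat intervention could move a scan close to day 200. These points lower the scan-only share but do not replace a dating rule.

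Finally, the sample size was not formally derived, the aim is a preliminary assessment, and sampling error of the benchmark matters at least as much as the half-scan-only effect. That limits the weight of this point. But the plan attaches a significance-based selection rule to these data, and the correction is cheap.

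**Conclusion.** The schedule conflict is established from the documents. Appendix B has no staging row between day 140 and the row beyond week 52 in either group, against Section 12.D, and the gap covers the 200-day benchmark. Under the text alone, scheduled scans at the maximum interval still fall on either side of day 200. It is also established that no dating rule and no historical scan frequency are given.

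A reader might go further and infer that the rule compares misaligned event times and that its false-positive rate is inflated. The documents do not support that. The historical patients come from the same centre's cohort and may have been dated in the same way, and the calculated direction depends on the schedule. With 84-day historical scans and half of lesions scan-only, the rate is above the exact-dating value for a last scan on day 133 or 147 and below it for day 161 or 175. With 182-day historical scans it is below on all four. There is also no single planned rate to exceed, because neither level is chosen and ≤3 events gives 17% even with perfect dating.

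The figures are therefore a sensitivity range. They rest on assumed curve shapes, scan-only shares and historical scan intervals, and on a reconstructed rule that does not reproduce all of Table 8. Scan timing is a possible, unquantified shift in either direction. This should be fixed, with medium confidence about its practical size.

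**What to change.** 1. Reconcile Appendix B with 12.D.1 and 12.D.2: add staging rows at most 12 weeks apart from day 140 through week 52 in both groups, and align Group 2 footnote d with follow-up until new metastasis.
2. Date new metastases by one method in the trial and in the 49 historical patients: the date of the detecting scan or examination, with an interval-censored median as a sensitivity analysis. Re-estimate the 200-day benchmark and Table 8 on that basis, and name the confidence-interval method and level.
3. If historical scan dates are unavailable, report the decision over a stated range of historical scan intervals (for example 84, 120 and 182 days) for each trial schedule.

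The cost is a text correction, one dating rule, and rework of 49 records from the centre's own cohort. The benchmark and the stated power may change, and incomplete historical scan dates would leave only the sensitivity range. The difference in time origin and the sampling error of the historical median would remain and need separate treatment.

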13. MANAGEMENT OF TOXICITIES AND COMPLICATIONS

13.A. Toxicity Grading

Toxicity grading will be evaluated according to the current guidelines in NCI Common Toxicity Criteria version 4.0.⁷⁷ The full text of the NCI CTCAE is available online at: <http://evs.nci.nih.gov/ftp1/CTCAE/About.html>.

13.B. Regimen Related Toxicity

If the patient develops excessive Toxicity attributable to one or more component of the regimen, the patient will not receive additional study treatment and a treatment of corticosteroids will be given, if clinically indicated (please refer to **Section 13.C**). Excessive toxicity will be considered when a non-pre-existing Grade 3 or higher toxicity develops after the start of treatment with the following exceptions:

13.B.1. Expected toxicities attributable to anti-PD-L1 (Avelumab) infusions and considered exceptions to criteria for discontinuation include:

1. Infusion-related reactions (see **Section 13.C** for management):
 - i. Transient (\leq 6 hours) Grade 3 CRS, flu-like symptoms or fever, which is controlled with medical management.
 - ii. Transient (\leq 24 hours) Grade 3 fatigue, local reactions, headaches, nausea, emesis that resolved to \leq Grade 1.
 - iii. Single laboratory values out of normal (excluding Grade \geq 3 liver function tests increase) that are unlikely related to Avelumab according to the investigator, do not have a clinical correlate, and resolve to \leq Grade 1 within 7 days with adequate medical management.
 - iv. Urticaria lesions responding to antihistaminics (Grade 2)
 - v. Allergic reaction (flushing or rash) responding to antihistaminic treatment (Grade 2).
2. Tumor flare phenomenon defined as local pain, irritation, or rash localized at sites of known or suspected tumor.

3. Tumor-lysis syndrome: If symptoms of tumor lysis occur after the Avelumab infusions they will be managed according to best clinical practice (see **Section 13.C.4**). Tumor lysis will not constitute a reason to discontinue the Avelumab infusions.
4. Change in ECOG PS to ≥ 3 that resolved to ≤ 2 within 14 days (infusions should not be given on the following cycle if the ECOG PS is ≥ 3 on the day of the Avelumab administration).

13.B.2. Expected toxicities attributable to **localized radiation** of pre-existing symptomatic metastasis and considered exceptions to criteria for discontinuation include:

- i. Non-life-threatening - diarrhea (i.e. 4-6 stools over baseline stools a day)
- ii. Target organ inflammatory responses resulting in Grade 3 or 4 toxicities that return to baseline within 4 weeks. For example: elevated lipase and/or amylase after radiation to a pancreatic lesion; or elevated transaminases after radiation to a liver lesion.
- iii. Hyperglycemia (Grade 3) lasting <14 days.
- iv. Dry skin, skin pain, and erythema lasting <14 days.
- v. Single laboratory values out of normal that according to the investigator do not have a clinical correlate and resolve to \leq Grade 1 within 7 days with adequate medical management.

13.B.3. Expected toxicities attributable to **intraleisional IFN β -1B injections** and considered exceptions to criteria for discontinuation include:

- i. Non-life-threatening infections (i.e. absence of hemodynamic compromise requiring pressor support and non-opportunistic infection).
- ii. CRS Grade 3 or less, including but not limited to asthenia, flu-like symptoms, myalgia, lymphopenia, and rigors.
- iii. Target organ inflammatory responses resulting in Grade 3 or 4 toxicities that resolve within 4 weeks. For example: elevated lipase and/or amylase after injection to a pancreatic lesion; or elevated transaminases after injection to a liver lesion.
- iv. Single laboratory values out of normal that according to the investigator do not have a clinical correlate and resolve to \leq Grade 1 within 7 days with adequate medical management.

13.B.4. Expected toxicities attributable to **T-cell infusions** and considered exceptions to criteria for discontinuation include:

- i. CRS Grade 3 or less, including but not limited to asthenia, flu-like symptoms, myalgia, lymphopenia, and rigors.
- ii. Skin rash or erythroderma (Grade 3 toxicity) lasting for <7 days.

- iii. Hypoxemia requiring continuous oxygen <72 hours, but not requiring mechanical ventilation or intubation.
- iv. Fever that resolves within 36 hours of the T-cell infusion.
- v. Lymphopenia (lymphocytes <500) that resolves to baseline levels (pre-therapy) within 4 weeks.
- vi. Single laboratory values out of normal that according to the investigator do not have a clinical correlate and resolve to ≤ Grade 1 within 7 days with adequate medical management.

13.C. Management of Symptoms During Avelumab Infusions

13.C.1. Special precautions

As infusion reactions have been observed with Avelumab (see **Section 3.J.3**), pre-treatment with H1 blockers (diphenhydramine 12.5-50 mg PO, IV, or equivalent), and acetaminophen (500 to 650 mg orally) will be administered 30 to 60 minutes prior to each Avelumab infusion to mitigate infusion-related reactions including hypersensitivity reactions. As a routine precaution, subjects enrolled in this trial must also be observed for 1 hour post infusion, in an area with resuscitation equipment and emergency agents.

Infusion of Avelumab will be stopped in case of Grade ≥ 3 hypersensitivity, inflammatory response, or infusion-related reaction. The treatment recommendations for infusion-related reactions, severe hypersensitivity reactions, and tumor lysis syndrome according to the NCI are as outlined in **Sections 13.C.2, 13.C.3, and 13.C.4** below.

13.C.2. Infusion-related reactions

A. Symptoms

- Fever
- Chills
- Rigors
- Diaphoresis
- Headache

B. Management

Table 5. Treatment modification for symptoms of infusion-related reactions caused by Avelumab

NCI-CTCAE Grade	Treatment Modification for Avelumab
Grade 1 – mild Mild transient reaction; infusion interruption not indicated; intervention not indicated.	Decrease the Avelumab infusion rate by 50% and monitor closely for any worsening. The total infusion time for Avelumab should not exceed 120 minutes.
Grade 2 – moderate Therapy or infusion interruption indicated but responds promptly to symptomatic treatment (for example, antihistamines, NSAIDs, narcotics, IV fluids); prophylactic medications indicated for \leq 24 hours.	Stop Avelumab infusion. Resume infusion at 50% of previous rate once infusion-related reaction has resolved or decreased in severity to < Grade 1, and monitor closely for any worsening.
Grade 3 or Grade 4 – severe or life-threatening Grade 3: Prolonged (for example, not rapidly responsive to symptomatic medication and/or brief interruption of infusion); recurrence of symptoms following initial improvement; hospitalization indicated for clinical sequelae. Grade 4: Life-threatening consequences; urgent intervention indicated.	Stop the Avelumab infusion immediately and disconnect infusion tubing from the subject. Subjects must be withdrawn immediately from Avelumab treatment and must not receive any further Avelumab treatment.

Definitions: IV=intravenous, NCI-CTCAE=National Cancer Institute-Common Terminology Criteria for Adverse Event, NSAIDs=nonsteroidal anti-inflammatory drugs,

Once the Avelumab infusion rate has been decreased by 50% or interrupted due to an infusion-related reaction, it must remain decreased for all subsequent infusions. If the subject has a second infusion-related reaction of Grade \geq 2 on the slower infusion rate, the infusion should be stopped and the subject should be removed from Avelumab treatment. If a subject experiences a Grade 3 or 4 infusion-related reaction at any time, the subject must discontinue Avelumab.

13.C.3. Management of severe hypersensitivity reactions and flu-like symptoms due to Avelumab infusions

If hypersensitivity reaction occurs, the subject must be treated according to the best available medical practice. Subjects should be instructed to report any delayed reactions to the Investigator immediately.

A. Symptoms

- Impaired airway
- Decreased oxygen saturation (< 92%)
- Confusion
- Lethargy
- Hypotension
- Pale / clammy skin
- Cyanosis

[figure not shown]
B. Management

1. Epinephrine injection and dexamethasone infusion
2. Patient should be placed on monitor immediately
3. Alert ICU for possible transfer if required

For prophylaxis of flu-like symptoms, 25 mg of indomethacin or comparable NSAID dose (for example, ibuprofen 600 mg, naproxen sodium 500 mg) may be administered 2 hours before and 8 hours after the start of each dose of Avelumab IV infusion. Alternative treatments for fever (for example, paracetamol) may be given to subjects at the discretion of the Investigator.

13.C.4. Tumor lysis syndrome

In addition, since Avelumab can induce antibody-dependent cell-mediated cytotoxicity (ADCC), there is a potential risk of tumor lysis syndrome. Should this occur, subjects should be treated per the local guidelines and the management algorithm below (**Figure 135**).⁷⁸

Definitions: TLS=tumor lysis syndrome

Figure 135. Assessment and initial management of tumor lysis syndrome
13.C.5. Delayed toxicities and immune-related adverse events (irAE) secondary to

Avelumab

Patients will also be closely monitored for potential irAEs,^{79,80} which may manifest earliest after weeks of treatment. Such events may consist of persistent rash, diarrhea and colitis, autoimmune hepatitis, arthritis, glomerulonephritis, cardiomyopathy, or uveitis and other inflammatory eye conditions. The spectrum of hypothetical irAEs also includes formation of auto-antibodies like anti-nuclear antibodies (ANAs) or antineutrophil cytoplasmic antibodies (ANCAs). IrAEs will be managed according to **Section 13.E** with steroids.

Suggested management for Grade 2 adverse drug reactions (ADR):

- If a Grade 2 ADR resolves to Grade ≤ 1 by the last day of the current cycle, treatment may continue.
- If a Grade 2 ADR does not resolve to Grade ≤ 1 by the last day of the current cycle, infusions should not be given on the following cycle. If at the end of the following cycle the event has not resolved to Grade 1, the subject should permanently discontinue treatment with a Avelumab ADR (except for hormone insufficiencies, that can be managed by replacement therapy; for these hormone insufficiencies, up to 2 subsequent doses may be omitted).
- Upon the second occurrence of the same Grade 2 ADR (except for hormone insufficiencies that can be managed by replacement therapy) in the same subject, treatment with Avelumab must be permanently discontinued.

13.D. Management of Symptoms During T-Cell Infusion

Immediate reaction to infusion (i.e. defined as those occurring either during the first 24 hours following T-cell infusion) may occur due to release of cytokines from T cells stimulated by the recognition of targets. Mild transient symptoms have been observed with lymphokine-activated killer cell (LAK) and TIL cell infusions, and with infusions of antigen-specific T-cell clones (**FHCRC Protocol 2140**).

13.D.1. Milder reactions (i.e. <Grade 3 CTCAE v.4 or less severe than specified below) would include symptoms such as:

- Fever, chills, fatigue.
- Dyspnea, chest tightness, or myalgia,
- Alteration in vital signs such as:
 - Lowering of blood pressure, but with systolic BP ≥ 90 mm Hg, or ≤ 20 mm Hg below baseline.
 - Tachycardia, but with HR ≤ 130 or ≤ 30 above baseline.
 - Tachypnea, but with RR $\leq 32/\text{min}$ or ≤ 10 above baseline.
 - Hypoxemia, but O₂ saturation $\geq 88\%$ on room air, or $\leq 5\%$ fall from baseline.
 - Skin changes such as erythema, urticaria, or other rash.

Management will be by **decreasing the rate of infusion and/or appropriate supportive care** such as:

- Acetaminophen or Demerol for fever and chills. (All subjects who develop fever or chills should have a blood culture drawn).
- Acetaminophen for headache.
- Diphenhydramine for nausea and vomiting.
- Fluid administration for hypotension.
- Supplemental oxygen for hypoxemia.

13.D.2. More severe reactions occurring during the 1-2 hour infusion would include symptoms such as:

- Hypotension with systolic BP <90 mm Hg and >20 mm Hg below baseline
- Tachycardia with HR >130 and >30 above baseline.
- Tachypnea with RR >32 and >10 above baseline.
- Hypoxemia with O₂ saturation of <88% and >5% fall from baseline.

Management will be by **terminating the infusion and administering supportive medical care**.

- If patient responds to supportive care by normalization of vital signs or resolution of hypoxemia and PI deems it safe to continue, the infusion will be restarted at slower rate.
- If the patient does not respond by normalization of vital signs or hypoxemia after supportive care alone, **methylprednisolone to ablate the infused T cells will be administered as per Section 13.E.**

13.D.3. Any unexpected severe toxicity (see Section 13.B) occurring in the first 24 hours (due to the T-cell infusion and not attributable to a non-infusion-related cause).

Management will be by **supportive medical care and methylprednisolone will be administered as per Section 13.E.**

13.D.4. Delayed toxicities secondary to T-cell infusions

Although unlikely, it remains possible that the infusion of MCPyV TAg-specific T cells will result in delayed toxicities related to the recognition of tumor tissue. It is anticipated that the symptoms and signs will occur within hours to four weeks after completion of the T-cell infusion.

Any toxicities requiring treatment discontinuation (see Section 13.B) occurring within 4 weeks of study treatment (potentially due to the T-cell infusion and not attributable to a non-infusion-related cause) **will be managed by supportive care and MP will be administered as per Section 13.E.**

13.E. Management of Severe Treatment-related Toxicities with Corticosteroids

- i. The patient will receive corticosteroids if treatment-related toxicity warranting ablation of T cells is observed.
- ii. The patient will be hospitalized for the first 48 hours for monitoring. The following dose schedule is recommended:

Day 1	Intravenous Methylprednisolone at 2 mg/kg
Day 2	Intravenous Methylprednisolone at 2 mg/kg
Day 3-4	Prednisone at 30 mg po b.i.d.
Day 5-6	Prednisone at 15 mg po b.i.d.
Day 7-8	Prednisone at 10 mg po b.i.d.
Day 9-10	Prednisone at 10 mg po q.d
Day11-12	Prednisone at 5 mg po q.d.

- iii. The *in vivo* frequency of infused CD8⁺ T cells will be assayed immediately prior to and between 48 and 72 hours after the start of steroid therapy.

13.F. Concomitant Therapy

13.F.1. As with all monoclonal antibody therapies, Avelumab carries a risk of allergic reaction. Avelumab will be administered at the SCCA in a setting that allows for immediate access and administration of therapy for severe allergic or hypersensitivity reactions, such as the ability to implement immediate resuscitation measures. Steroids (dexamethasone 10 mg), epinephrine (1:1000 dilution), allergy medications (antihistamines), or equivalents are available for immediate access. If hypersensitivity reaction occurs, the subject must be treated according to the best available medical practice.

13.F.2. Subjects will be pretreated with H1 blockers (diphenhydramine 25-50 mg PO or IV, or equivalent), and acetaminophen 500 to 650 mg (orally), 30 to 60 minutes prior to each Avelumab and T-cell infusion.

13.F.3. Any medications (other than those excluded by the clinical trial protocol) that are considered necessary for the subjects' welfare and will not interfere with the IMP may be given at the Investigator's discretion. For example, active infections occurring after initiating the study should be treated according to the standard of care. Other agents might include analgesics, antinausea medications, antihistamines, diuretics, anti-anxiety medications, and medication for pain management, including narcotic agents.

13.F.4. The following agents are not allowed while on study:

- Systemic corticosteroids (except as outlined for management of toxicity of Avelumab and non-transduced CTL)
- Immunotherapy (for example, interleukins, MCC vaccines, intravenous immunoglobulin, expanded polyclonal TIL or LAK therapy)
- Pentoxifylline, other small-molecule or chemotherapy cancer treatment
- Other investigational agents
- Any vaccine therapies for the prevention of infectious disease (for example, seasonal flu vaccine, human papilloma virus vaccine) except administration of the inactive influenza vaccine
- Growth factors (granulocyte colony stimulating factor or granulocyte macrophage colony stimulating factor). Exception: erythropoietin and darbepoietin alpha may be prescribed at the Investigator's discretion
- Bisphosphonate treatment is not allowed unless it has been initiated more than 14 days prior to receiving the first administration of Avelumab

13.G. Off-study Criteria

A patient's participation on the protocol will be terminated for any of the reasons listed below:

- Progressive disease or development of new metastasis requiring urgent additional drugs (for example chemotherapy)
- The participant withdraws consent
- Patient death
- Occurrence of pregnancy
- Participation in another trial during the treatment duration of this trial
- Occurrence of an exclusion criterion, which is clinically relevant and affects the subject's safety, if discontinuation is considered necessary by the Investigator or Sponsor
- A patient will no longer be eligible to receive additional therapy if the PI or his designee determines that additional T cell and / or avelumab infusions are not in the best interest of the patient
- Occurrence of any non-pre-existing AEs / repetitive Grade 2 AEDRs that are deemed related to the treatment as defined in **Section 13.C.2.**

- Use of a non-permitted concomitant drug such as steroids, or as defined in **Section 13.F.4** for which the predefined consequence is withdrawal from the trial
- The reasons for premature discontinuation must be recorded on the case report form. The patient may re-enter the study after premature discontinuation only by approval of the PI

